Pharmacologic and surgical therapeutic options for ankle osteoarthritis are limited. Treatments have traditionally consisted of temporizing measures such as physical therapy and topical, oral and intra-articular pharmaceutical therapies until operative treatment with either arthrodesis

or arthroplasty is required. Cryoneurolysis is a specialized technique for providing long-term pain relief in interventional pain management settings⁵. Treated nerves are temporarily blocked from transmitting pain signals, followed by functional recovery after a time period.

Using cryoneurolysis in patients with ankle OA could potentially provide immediate symptomatic relief with a greater duration of analgesia and a lower rate of side effects than other non-operative treatments. These potential benefits could reduce the need for both clinic and injection visits when compared to other treatment modalities, thereby reducing patient and provider burden and health care expenditures.

The iovera[°] device is 510(k)-cleared (K133453 and K161835) and is used to destroy tissue during surgical procedures by forming a precisely controlled, sub-dermal cold zone. It can also be used to produce lesions in peripheral nervous tissue by forming a precise cold zone of -20 to -88.5 degrees Celsius to temporarily disrupt peripheral nerve function, ultimately blocking pain.¹ It is also indicated for the relief of pain and symptoms associated with osteoarthritis of the knee for up to 90 days. The iovera[°] system is not indicated for treatment of central nervous system tissue.

The iovera[°] device uses liquid nitrous oxide (N₂O) that is contained within the handpiece. This pressurized liquid travels from the hand-piece to the closed-end needles of the smart tip, where it undergoes a phase change, forming a precise cold zone. The gaseous nitrous oxide is expelled out of the hand-piece, leaving nothing behind in the body. This treatment causes a temporary nerve block based on a process called Wallerian degeneration or 2nd-degree nerve injury. This degeneration affects the axon and myelin sheath while leaving the surrounding nerve components intact such as the endoneurium, perineurium or epineurium Figure 1. When sensory nerves are treated, their ability to convey sensory signals, such as pain, is immediately interrupted.

Structure of a Nerve – Note that all nerves contain both myelinated and unmyelinated sensory and motor fibers (axons)

[figure not shown]

Figure 1

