A FAOS validation study, completed by S.B.Mani et al., confirmed that some FAOS sub-scales (i.e. pain, activities of daily living and quality of life) are valid for independent use. According to the study, the effect size for FAOS pain and quality of life is 1.06, whereas for activities of daily living there is an effect size of 0.65. At an effect size of 0.65 and a single-sized alpha of 0.025, a sample size of 32 would provide a power of 90%. While 80% power is customary, it would be desirable to plan for 90% to reduce the probability of missing an effect if one is present and to provide sufficient power for comparisons at 2-time points. Assuming up to 20% dropout, we plan to recruit 40 participants. This should be more than sufficient, considering that the effect size for the other 2 outcomes has been reported to be 1.06.⁹

D. Subject Criteria (See Vulnerable Populations appendix, if applicable):

Enrollment will be comprised of 40 subjects, age 18 and over with symptomatic ankle OA. There will be no exclusions based on sex or ethnic group. Potential subjects will be identified through hospital records, referrals from physicians in the surrounding community, and mass mailings, or advertisements posted in area clinics and businesses.

1. Inclusion criteria

- Participation in an institutional review board-approved informed consent process, culminating in providing written consent.
- Willingness and ability to comply with the study procedures, visit schedules and ability to follow verbal and written instructions.
- Male or female over 18 years of age.
- Currently Kellgren-Lawrence (KL) Grade 2, 3 or 4 in the ankle based on an X-ray. (weight-bearing mortise views with 20° internal rotation)¹⁰
- Limited by unilateral ankle pain, rated on a Numerical Rating Scale for pain severity as ≥5 on most days over the last month.
- Foot and ankle outcome score (FAOS) of < 75 in at least 1 category.
- Body mass index (BMI) ≤ 50 kg/m²
- Ambulatory.
- Willingness to abstain from the use of protocol-restricted medications during the study and also willing to abstain from using analgesics other than acetaminophen 1 week prior to the beginning of the study.
- Has undergone at least one prior conservative osteoarthritis treatment (e.g. physical therapy, analgesics).

2. Exclusion criteria:

- Baseline knee, hip, spine or other limitations that affect the walking ability to a greater extent than their ankle.

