- Cryoglobulinemia, paroxysmal cold hemoglobinuria, Raynaud's disease, cold urticaria.
- Clinical signs or symptoms of active or recurrent infection in the index ankle joint or overlying skin.
- IA corticosteroid (investigational or marketed) within 3 months of screening.
- Oral corticosteroids (investigational or marketed) within 2 weeks of screening (unless on a chronic stable dose for ≥ 3 months prior to enrollment).
- Women who are pregnant (due to potential for the change in body mass and distribution to alter ankle symptoms over the period of follow-up).
- Any condition other than OA of the ankle joint which, in the opinion of the investigators, affects their ability to ambulate to a sufficient degree or interferes with the assessment of the safety and treatment effects of the study injection.
- Arthroscopy or open surgery of the ankle joint within 6 months of screening.
- Planned/anticipated surgery of the index ankle joint during the 6-month study period.
- Any clinically significant degree of cognitive impairment or other condition, finding, or psychiatric illness at screening which, in the opinion of the investigator, could compromise patient safety or interfere with the assessment of the safety and treatment effects of the study injection.
- Skin breakdown at the ankle joint where the injection is planned to take place.
- Participated in any investigational drug or device trial within 30 days prior to screening or concurrent participation in another research study that could complicate interpretation of the findings of either study.
- Current consumption of more than 14 alcoholic drinks per week
- Patients with diffuse pain conditions (Complex pain - diffuse or confounding pain, fibromyalgia, etc).
- Known altered nerve anatomy or physiology (e.g. neuropathy) at the target, such as due to a congenital, traumatic, medical or surgical cause.

3. Withdrawal/Termination criteria:

Subjects may discontinue the study at any time. The investigator may discontinue a subject at any time for subject safety or noncompliance. Subjects who are discontinued for safety will be referred to their primary care physician for follow-up.

The Investigator/Coordinator will complete a study exit form in the CRF for any subject who prematurely discontinues from the study. If discontinuation was the result of an AE, the AE will also be recorded in the CRF.

4. Allowable Medications/Nonpharmacological Therapies

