The following medications and nonpharmacological therapies may be taken or used throughout the study:

- Aspirin for cardio-protection at a maximum stable dose of 100 mg per day provided the dose was stabilized over 3 months prior to study entry.
- Physical therapy/bracing for the ankle joint if the program was initiated and consistent prior to study entry.
- Acetaminophen as an occasional rescue medication. Concomitant treatment for OA will be standardized to oral acetaminophen (e.g. Tylenol) for all subjects during the study. During the screening period (i.e., prior to the procedure visit), subjects may take acetaminophen as needed to a maximum of 3000 mg per day. Use of acetaminophen must be discontinued 48 hours prior to the procedure visit and each subsequent scheduled visit.
- The use of acetaminophen for other types of pain or illness during the study (e.g., toothache, headache, fever) should also be recorded.

5. Restricted Medications/Nonpharmacological Therapies

Patients will be asked to abstain from certain medications and therapies. The following medications and nonpharmacological therapies should not be taken or used beginning immediately upon enrollment (after signing informed consent) until the subject reaches the end of the study:

- Oral non-steroidal anti-inflammatory drugs (NSAIDs) (unless on a chronic stable dose for ≥ 3 months prior to enrollment).
- Topical analgesics applied to the skin over the index ankle (e.g., NSAID's, capsaicin, lidocaine, heat patches).
- Orally administered systemic corticosteroids (unless on a chronic stable dose for ≥ 3 months prior to enrollment).
- Intra-articular injection into the ankle or subtalar joints.
- Centrally acting pain medications (unless on a chronic stable dose for ≥ 3 months prior to enrollment).
- Opioid medications (unless on a chronic stable dose for ≥ 3 months prior to enrollment)

E. Specific methods and techniques used throughout the study

Primary Outcome

The Foot and Ankle Outcome Score (FAOS), derived from the validated Knee Injury and Osteoarthritis Outcome Score (KOOS). It is a region-specific questionnaire that has been well described and validated.^{9 11}

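### The pre-entry injection look-back covers only intra-articular corticosteroid, so another recent ankle injection can carry over into an uncontrolled change from baseline

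*Combined protocol and SAP*

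**What the plan says.** Section II.D.2 (Exclusion criteria) gives one look-back for injections: "IA corticosteroid (investigational or marketed) within 3 months of screening". Other pre-entry limits apply to other treatments. In II.D.2 these are "Oral corticosteroids (investigational or marketed) within 2 weeks of screening" (with an exemption for a long-standing stable dose), "Arthroscopy or open surgery of the ankle joint within 6 months of screening" and "Participated in any investigational drug or device trial within 30 days prior to screening". In II.D.1 (Inclusion criteria) the participant must be "willing to abstain from using analgesics other than acetaminophen 1 week prior to the beginning of the study".

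Section II.D.5 (Restricted Medications/Nonpharmacological Therapies) lists "Intra-articular injection into the ankle or subtalar joints" without limiting the product. That list takes effect once consent is signed and runs to the end of the study. It does not look back.

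Section II.D.4 (Allowable Medications/Nonpharmacological Therapies) permits "Physical therapy/bracing for the ankle joint if the program was initiated and consistent prior to study entry". No length of time is attached. The drug rules in II.D.4 and II.D.5 (aspirin, oral NSAIDs, oral corticosteroids, centrally acting drugs, opioids) all use a 3-month stability period.

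The background section (I.B) describes usual care as "temporizing measures such as physical therapy and topical, oral and intra-articular pharmaceutical therapies", so intra-articular products are part of the setting that the protocol itself describes.

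Section II.C states that there is no control group, and II.E defines the primary endpoint as FAOS-Pain at 12 weeks compared with baseline.

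**The concern.** The in-study ban shows that the plan regards any intra-articular ankle or subtalar injection as something that could disturb its results. The entry criteria guard against only one kind. An injection of another marketed product a few days before consent is admitted; the same injection a few days after consent is prohibited.

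In a controlled trial such carry-over would tend to fall on both arms. Here the whole change from baseline is read as the result of cryoneurolysis, so eligibility and concomitant-therapy rules are the main protection. An earlier injection still taking effect would flatter the mean change, and one wearing off would hide benefit. The same carry-over would enter the NRS-based responder status in II.B, which is also judged against baseline and decides who is offered the second nerve treatment.

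The undefined period for physical therapy and bracing raises the same question in a weaker form.

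**Working it through.** **Step 1. Pre-entry and in-study rules side by side.**

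| Treatment | Before entry | During the study |
|---|---|---|
| IA corticosteroid | 3 months before screening | barred in ankle or subtalar joint |
| Other IA ankle or subtalar injection | no limit | barred from consent |
| Ankle surgery | 6 months before screening | planned surgery is an exclusion |
| Oral corticosteroid | 2 weeks, or stable for at least 3 months | barred unless stable for at least 3 months |
| Analgesics other than acetaminophen | 1 week | several classes barred, most with a 3-month stability exemption |
| Investigational products | 30 days, through trial participation | concurrent participation limited |
| Ankle physical therapy or bracing | begun and consistent; no period | may continue |

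The second row is the only one with an in-study ban and no pre-entry limit. The last row has a condition with no stated length.

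**Step 2. Would another criterion stop the person?** Take someone given a marketed non-corticosteroid ankle injection one week before screening.
- The 30-day rule concerns trial participation, so a marketed injection in ordinary care is not caught.
- The pain criterion in II.D.1 asks for NRS of at least 5 on most days of the preceding month. Someone who responded several weeks ago would probably fail it. Someone injected a week ago can satisfy it on the days before the injection and improve afterwards. The mitigation is partial.
- The investigator-judgement exclusions in II.D.2 are written about conditions, findings and illness. They do not clearly reach a recent treatment.

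**Step 3. When is baseline taken?** In the first-treatment schedule (II.E), FAOS is collected at screening and not at the treatment visit, and II.B allows up to 21 days between the two. Change caused by an earlier injection in that gap also counts towards the endpoint.

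**Step 4. Size in points.** The documents give no frequency and no carry-over effect, so both are assumed. With k of N participants affected by d points each, the shift in the mean is k × d / N:
- k = 2, d = 10: 2 × 10 / 40 = 0.5 points
- k = 4, d = 15: 4 × 15 / 40 = 1.5 points
- k = 6, d = 20: 6 × 20 / 40 = 3.0 points

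A waning effect gives the same sizes with a negative sign. The protocol gives neither a standard deviation nor a clinically important difference for FAOS-Pain, so these points cannot be set against a benchmark of its own.

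**Step 5. Size as false-positive risk.** Suppose cryoneurolysis has no effect and a share f improves by e SD from an earlier or ongoing treatment. The mean shift is f × e SD, with the SD held at 1. For a one-sample t-test with N = 32 and one-sided alpha 0.025 (both from II.C), the chance of a significant result comes from a noncentral t with noncentrality f × e × √32. For f = 10% and e = 0.5 this is 0.05 × 5.657 = 0.283.

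| f | e (SD) | Shift (SD) | Chance of significance |
|---|---|---|---|
| 0 | – | 0 | 2.5% (nominal) |
| 10% | 0.3 | 0.03 | 3.6% |
| 10% | 0.5 | 0.05 | 4.6% |
| 10% | 0.8 | 0.08 | 6.4% |
| 20% | 0.5 | 0.10 | 7.9% |

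For scale, II.C quotes an effect size of 1.06 for FAOS-Pain. A shift of 0.05 SD is 0.05 / 1.06 = 4.7% of that, and 0.10 SD is 0.10 / 1.06 = 9.4%.

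**The case against.** The best defence has several parts.

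- **The main injection is covered.** Corticosteroid is the only injection the protocol names as standard of care (I.A), and it has a 3-month limit. Other products appear only as a general mention in I.B and in the title of one cited paper on platelet-rich plasma. This stands as an argument about frequency; it does not close the gap.
- **A ban and a washout serve different purposes.** This also stands. The two sections differ in scope, but a reader who inferred that they contradict each other would go too far. What is missing is a reason for the difference.
- **Consistent already implies stability.** Largely right. A reader might infer that a program begun the week before entry plainly qualifies; the wording does not support that, because it asks for more than a start date. The fair criticism is that the term has no stated period.
- **The lack of a control arm is the larger threat.** True, and II.C states it openly for a pilot study. Placebo response and regression to the mean would remain after any change here. That does not argue against removing an avoidable source of bias at little cost.
- **Three months is only one of several windows in the plan**, which run from 1 week to 6 months. Also true. It is suggested because the plan already applies it to the one injection it limits, and the sponsor may justify another period.

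**Conclusion.** The gap for non-corticosteroid injections is real. The plan admits before consent what it prohibits after consent, and a single-arm change from baseline cannot separate the two effects. The gap for therapy and bracing is an undefined term and is secondary.

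The likely size is modest: 0.5 to 3.0 points on a 0 to 100 scale, in either direction, resting wholly on an assumed 2 to 6 affected participants and 10 to 20 points each. The upper figure needs both extremes together.

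Three stronger readings are tempting, and the documents do not support them:
- That recent ankle treatment in general is uncontrolled. Surgery, oral corticosteroids, analgesics and investigational trials all have pre-entry limits.
- That the result will be inflated. A waning injection would bias it downwards.
- That the requirement for at least one prior conservative treatment (II.D.1) makes recent treatment likely. It says nothing about timing, and analgesics satisfy it.

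This is a worthwhile, inexpensive tightening of eligibility. It does not invalidate the design and does not change the sample size.

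**What to change.** 1. **Injections.** Reconcile II.D.2 with II.D.5. Keep the corticosteroid exclusion as it is (it names no joint) and add that any intra-articular injection into the index ankle or subtalar joint within the same 3 months before screening excludes. If the narrower criterion is intended, state why.
2. **Therapy and bracing.** In II.D.4, give the period over which a program must have been consistent, in line with the 3-month stability wording used for drugs in the same sections.
3. **Participants already enrolled.** The visit changes for March to May 2020 in II.B suggest there are some. Use the prior/concurrent therapy record taken at screening to describe recent and ongoing ankle treatment, and add to V.A a sensitivity analysis of 12-week FAOS-Pain that leaves out those with a recent non-corticosteroid injection or newly started therapy or bracing. Fix the definitions of recent and newly started before outcomes are examined. The schedule does not say whether dates and products are recorded, so check this first. Report which participants entered under which wording.

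**Cost.** Protocol wording and one added analysis. A few candidates wait or are lost. No new procedures or visits are needed.

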FAOS (Pain, ADL, QoL), NRS for pain and physical performance tests (40 m fast paced walking test and, Standing Balance Test) will be assessed at baseline and 6, 12, and 24 weeks post-treatment. Phone calls at 3, 9 and 18 weeks post-treatment will monitor subjects using the NRS pain scale.⁷ Electronic data capture will be used for this study. Adverse events will be monitored at each telephone call and follow-up visit. There will be a grace period of 21 days between the screening and treatment visit. There is a +/- 3-day window for follow-up visits. During the time period of March to May, 2020(depending on duration of suspension of non-essential research), we are modifying the protocol to conduct virtual study visits to address the COVID-19 pandemic. The following data points will be or will not be collected during this time as per the individual circumstance: 40mFPWT or Standing Balance test at 6 week, 12 week, and 24 week. In order to ensure subject safety and welfare we will conduct the 6 week, 12 week and 24 week f/u visit remotely for each treatment arm as per KU essential research guidelines. We will also offer participants masks, gloves, and complete the f/u visit at the

earliest to limit any potential exposure to people in the hospital. In order to address data integrity issues, we will try to conduct the 12 week f/u visits in person.

[figure not shown]

Figure 2 – Protocol flowchart depicting criteria for responders and non-responders at each follow up time point.

C. Sample size and power calculation

In this open-label study, participants will undergo cryoneurolysis using iovera. FAOS (Pain, ADL, QoL), NRS for pain and physical performance tests (40m fast-paced walking test and Standing Balance Test) data will be collected at baseline and 6, 12 and 24 weeks post-treatment. A 24-week follow-up duration was selected to detect meaningful differences from standard of care and long-term effects. A control group will not be included in this initial pilot study. Differences between each of the three follow-up time points and baseline will be assessed using one-sample t-tests or repeated measures analyses, as appropriate, controlling for study-wide alpha level to account for multiple comparisons as well as 6-week and 24-week analyses.

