The Standing Balance Test outcome is measured with the feet side by side, then in semi-tandem stance (heel of one foot in front and beside the big toe of the other foot), and then in tandem stance (heel of one foot directly in front of the other foot); each stance was held for up to 10s. These test results are converted to scores (range 0-4). Higher scores represent better function and a score of 0 represents the inability to complete the test. Subjects are given a score of 1 if they can hold a side-by-side standing position for 10 s but are unable to hold a semi-tandem position for 10s, a score of 2 if they can hold a semi-tandem position for 10s but are unable to hold a full tandem position for more than 2s, a score of 3 if they can stand in the full tandem position for 3-9s, and a score of 4 if they can stand in the full tandem position for 10s.¹³ The Standing Balance Test will be completed by the Subject and will take approximately 2 minutes to complete. The study coordinator or designee will enter the data into the eCRF.

The tables below depict the schedule of study assessments, or procedures, for each visit for the intervention(s) offered (superficial and/or deep).

Assessment	Visit 1 / Screening	Visit 2 / iovera[®] Treatment -1	Telephonic 3 Week Follow-up	Visit 3 / 6 Week Follow-up	Telephonic 9 Week Follow-up	Visit 4 / 12 Week Follow-up	Telephonic - 18 Week Follow-up	Visit 5 / 24 Week Follow-up
Informed Consent	X							
Eligibility	X	X						

Radiograph or SCT (if not previously done)	X							
Medical history	X	X						
Concomitant medications	X	X		X		X		X
Prior/Concurrent Therapy	X							
Study Treatment		X						
Physical Exam	X	X						
FAOS Questionnaire	X			X		X		X
NRS for Pain	X	X	X	X	X	X	X	X
Physical Performance Measures	X			X		X		X
AE/SAE Assessment		X	X	X	X	X	X	X

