 - g. Drawing / collecting laboratory specimens: N/A
 - h. Performing / conducting tests, procedures, interventions, questionnaires: [name]/[name]/[name]
 - i. Completing study data forms: [name]/[name]/[name]
 - j. Managing study database: [name]/[name]

L. Assessment of Subject Safety and Development of a Data and Safety Monitoring Plan

Compliance reports will be reviewed by the Principal Investigator on a weekly basis.

Reports containing the proportion of subjects completing the intervention or prematurely terminating participation will be generated monthly.

Adverse event information will be collected during all contacts with subjects. If an adverse event is reported to study staff, data including the type of event, onset/end dates, duration, severity, and outcome will be collected and reported to the Principal Investigator, who will determine severity of the event using CTCAE guidelines. Post-treatment expected symptoms include numbness of the skin over the ankle and foot and possibly redness, swelling, bruising or pain at the site of insertion.

An event that is serious must be recorded on the AE worksheet and requires expeditious handling to comply with regulatory requirements. Any adverse events classified as "serious" by the Investigator must be reported to the IRB within 24 hours of becoming aware of its occurrence.

III. Subject Participation**A. Recruitment:**

Potential study participants will be recruited from a HERON generated list, the clinics of the participating investigators, as well as local advertising. Any study-related advertisements will be approved by the governing IRB prior to use. Subjects will be recruited based upon inclusion and exclusion criteria detailed above. Participants will be compensated for their time and effort at follow-up visits.

Each subject will participate for up to 24 weeks following either deep or superficial nerve treatment. Enrollment is expected to take up to 6-12 months following (superficial or deep nerve) treatment. Total study duration is expected to be up to 18 months.

B. Screening Interview/questionnaire: Potential subjects who express interest in the study will be screened by telephone. A script will be used to determine eligibility for the first screening clinic visit by study staff. Please see Appendix II.

C. Informed consent process and timing of obtaining of consent

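### Discontinuation for safety is handled as study exit with no planned contact afterwards, so a treated subject may lose the remaining scheduled adverse event contacts (at most 6 per course)

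*Combined protocol and SAP*

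**What the plan says.** Section II.D.3 (Withdrawal/Termination criteria) allows the investigator to discontinue a subject for safety or noncompliance. For the safety case it gives one follow-up instruction: "Subjects who are discontinued for safety will be referred to their primary care physician for follow-up". It also says: "The Investigator/Coordinator will complete a study exit form in the CRF for any subject who prematurely discontinues from the study". An AE that led to discontinuation is entered in the CRF. The section says nothing about later study contact with such a subject.

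AEs are otherwise gathered at study contacts. Section II.B says: "Adverse events will be monitored at each telephone call and follow-up visit". Section II.L says: "Adverse event information will be collected during all contacts with subjects". Both schedule tables in Section II.E carry a row "AE/SAE Assessment", marked at the procedure visit and at weeks 3, 6, 9, 12, 18 and 24.

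For any AE reported to study staff, Section II.L requires that "data including the type of event, onset/end dates, duration, severity, and outcome will be collected". It makes no exception for subjects who have left the study.

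**The concern.** Each treatment course is a single procedure. Once it has been done, there is little study activity left for a safety decision to stop: a possible treatment of the other nerve group (Section II.B), the walking and balance tests, and the medication rules in Sections II.D.4 and II.D.5, such as "Use of acetaminophen must be discontinued 48 hours prior to the procedure visit and each subsequent scheduled visit". None of these requires AE calls to end. Yet the rule as written deals with the subject only by exit form and outside referral, so for a treated subject the main thing that ends is observation.

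What is at stake is whether and when an event open at exit resolved. Section II.F.1 names altered sensation as a risk and loss of motor function outside the target area as a complication that correct use can help prevent. The treatment is described as temporary in its effect on the nerve, so the resolution of a sensory or motor event is useful safety information. It may go missing in the subjects for whom safety was the reason to stop.

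**Working it through.** **Inputs**

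- Telephone contacts per course: weeks 3, 9 and 18, so 3 (Section II.B).
- Clinic visits per course: weeks 6, 12 and 24, so 3 (Section II.B).
- Recruitment of 40 with up to 20% dropout (Section II.C).

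**Count of scheduled AE contacts**

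The AE row has 7 marks in the first-treatment table and 7 in the second-treatment table. One of the 7 is the procedure visit, so 7 − 1 = 6 follow the procedure. This agrees with 3 calls + 3 visits = 6.

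**Contacts remaining after exit**

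Contacts remaining = number of scheduled weeks later than the week of exit.

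| Exit at | Contacts remaining |
|---|---|
| Procedure visit | 6 |
| Week 3 | 5 |
| Week 6 | 4 |
| Week 9 | 3 |
| Week 12 | 2 |
| Week 18 | 1 |
| Week 24 | 0 |

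These are upper bounds on the loss. They assume that nobody contacts the subject again after exit. Exit before any cryoneurolysis is not at issue.

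**The two rules side by side**

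Section II.L requires end date, duration and outcome. For an AE open at exit, all three become known only later. Section II.D.3 plans no later contact and does not ask the primary care physician to report back. The requirement stands, but the plan gives staff no scheduled occasion on which to meet it.

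**Ceiling on the cost of keeping the contacts**

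The documents give no number of subjects stopped for safety. As an extreme assumption, let every dropout in the plan's allowance be a treated subject stopped for safety at the procedure visit:

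- Subjects: 0.20 × 40 = 8.
- Calls: 8 × 6 = 48.
- Already telephone contacts (weeks 3, 9, 18): 8 × 3 = 24.
- In place of clinic visits (weeks 6, 12, 24): 8 × 3 = 24.

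The plan has already accepted remote contact at those clinic visits during the pandemic period: "we will conduct the 6 week, 12 week and 24 week f/u visit remotely for each treatment arm". All 48 are contacts these subjects would have had without exit, so none is added to the planned schedule. The figure of 48 bounds the cost of the change; it does not measure harm.

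**The case against.** The strongest case against runs as follows. No sentence says that contacts stop at exit. Referral to primary care assigns clinical care and does not bar study staff from calling. Section II.L collects AE information at any contact, scheduled or not, and its required fields apply to exited subjects too, so meeting that duty already implies seeking later information. Exit is at the investigator's discretion: an AE does not trigger it, and by default a treated subject with an AE stays on the 24-week schedule. The exit form, AE worksheet and consent form are not shown and may cover the point. In the knee trial cited in Section I.B, most expected side effects were mild and gone within 30 days, so cases may be few.

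Most of this stands, and it limits the claim. A reader might infer that a safety-discontinued subject is certain to lose all further AE observation. The documents do not support that: the loss is inferred from the exit wording together with silence elsewhere, and 6 contacts is the maximum. A reader might also infer that AE rates or serious-event reporting are compromised. That is not supported either: the event behind the exit goes into the CRF, severity is graded, and serious events still go to the IRB within 24 hours. Nor does the claim in Section I.B to be the first systematic evaluation raise the safety stakes, because that sentence concerns symptomatic and functional benefits.

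What the objection does not supply is a planned contact. A duty to record an outcome, with no stated time or person to obtain it, can easily go unmet once the subject has been exited and referred elsewhere.

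**Conclusion.** The point holds in limited form. Section II.D.3 treats safety discontinuation as study exit and does not distinguish ending procedures from ending safety observation. A treated subject may lose between 1 and 6 scheduled AE contacts in that course, depending on when exit falls before week 24. The end date, duration and outcome of an AE open at exit may go uncollected.

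This rests on two assumptions: that staff follow the rule as written and make no unscheduled contact, and that the forms not shown add no follow-up instruction. The number of subjects affected cannot be derived from the documents and is likely to be small. Incidence, severity and serious-event reporting for events known at exit are not affected, and no endpoint, sample size or power figure changes. The change is worth making because it is specific and cheap and improves the safety record of subjects stopped for safety; it is not a defect that threatens the trial.

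**What to change.** In Section II.D.3, define two separate decisions: no further study procedures, and withdrawal from follow-up. Then state that:

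- A treated subject stopped for safety has no further cryoneurolysis or performance testing and is released from the restrictions in Sections II.D.4 and II.D.5, including the 48-hour acetaminophen stop, as clinically needed.
- Unless consent is withdrawn, the subject keeps the remaining scheduled AE contacts by phone through week 24 after the last procedure.
- Any AE open when procedures stop is followed in those calls until resolved, judged stable or week 24, with the end date and outcome entered in the CRF.
- The primary care referral is kept in addition.

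The cost is protocol and consent wording plus at most 6 phone calls per affected subject. All of them fall within the existing schedule, so follow-up is not extended and no procedure is added.
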